12.4.4 Sensitivity and supportive analyses

In order to assess the robustness of the primary endpoint, sensitivity and supportive analyses are planned. These may include, but are not limited to:

- Imputation of missing data :
 - Considering missing data as disease activity
 - LOCF imputation
- Repetition of the primary analysis using the PPS.

Sensitivity estimand in exposed and non-exposed to the urgent safety measures: As a sensitivity analysis for the disease activity at Week 16, the proportion of subjects with no disease activity at Week 16 will be compared before and after the urgent safety measures were introduced. The analyses will be performed in FAS and PPS.

Further details about the analyses will be given in the SAP. Any major discrepancies in the results across analyses will be investigated as needed.

Age, baseline fluids type (IRF, SRF), number of previous antiVEGF injections, and time since nAMD diagnosis subgroup analyses will also be performed on the primary endpoint.

12.5 Analysis of secondary endpoints

All secondary efficacy analyses will be based on the FAS. The analyses performed at eye level will focus on the study eye only.

12.5.1 Effects of brolucizumab 6 mg on disease activity

The number (%) and proportion of subjects with no disease activity up to Week 48 will be provided.

12.5.2 Effect of brolucizumab 6 mg on anatomical parameters

Summary statistics of the change from Baseline in CSFT up to Week 48 will be provided.

The number (%) and proportion of subjects with absence of IRF, SRF, and sub-RPE fluid as assessed by OCT over time up to Week 48 will be presented.

The number (%) and proportion of subjects with dry retina (no IRF nor SRF) up to Week 48 will be presented.

12.5.3 Durability of brolucizumab 6 mg

Summary statistics of the time (in days) of the last interval with no disease activity before or at Week 48 will be provided. If there is disease activity, the last interval will be shortened by 4 weeks down to a minimum of 4 weeks. The distribution of the last interval is the proportion of subjects with no disease activity (Q4, Q8, and Q12) up to Week 48.

Summary statistics of time (in days) of the longest interval of treatment with no disease activity before or at Week 48 will be provided. The distribution of the maximal interval is the proportion of patients with no disease activity (Q8, Q12 and Q16) up to Week 48.

12.5.4 Functional outcomes

Summary statistics of the average change from Baseline in BCVA at Week 48 will be provided.

12.5.5 Safety endpoints

The Safety Set will be used for all safety analyses.

The secondary safety endpoint of this study is as follows:

- Incidence of AEs (serious and non serious) reported in patients treated with brolucizumab.

Safety summaries (tables, figures) include only data from the on-treatment period with the exception of Baseline data, which will also be summarized where appropriate (e.g. change from Baseline summaries). In addition, a separate summary for death including on treatment and post treatment deaths will be provided. In particular, summary tables for adverse events of special interest (AESIs) will summarize only on-treatment events, with a start date during the on-treatment period (treatment-emergent AEs).

The on-treatment period lasts from the date of first administration of IVT injection of study treatment to 30 days after the date of the last actual administration of IVT injection of study treatment.

12.5.5.1 Adverse events

Summary tables for AEs will summarize only on-treatment events with start date during the on-treatment period. Separate summary tables will be provided for AEs of the study eye, the fellow eye, and for non-ocular AEs.

The on-treatment period lasts from the date of first administration of study treatment to 30 days after the last administration of study treatment or EOS whichever is the latest.

All information obtained on AEs will be displayed by patient. All collected AEs will be listed.

[figure not shown]
The number (%) of patients with treatment-emergent AEs will be summarized in the following ways:

- by visit, primary system organ class and preferred term.
- by visit, primary system organ class, preferred term and maximum severity.

Separate summaries will be provided for AEs related to study medication, deaths, SAEs, AESIs and other AEs leading to discontinuation.

The number (%) of patients with AEs of special interest will be summarized by visit, primary system organ class and preferred term.

A patient with multiple AEs within a primary system organ class will only be counted once towards the total of the primary system organ class.

12.7 Interim analyses

An interim analysis will be performed when the last patient included completed Week-16 visit. Patients will remain in the study and will continue to receive treatment through the maximum planned duration of treatment of 44 weeks to allow for further evaluation of efficacy and safety.

12.8 Sample size calculation

The sample size calculation is based on the hypothesis of 25% to 35% of patients with no disease activity at Week 16. The sample size analyses were performed before the urgent safety measures were introduced.

Table 12-1 Confidence intervals for proportions (2 sided)

Confidence level	Sample size (N)	Expected proportion	Target distance from proportion to limit
0.950	250	0.25	0.054
0.950	300	0.25	0.049
0.950	325	0.25	0.047
0.950	400	0.25	0.042
0.950	250	0.30	0.057
0.950	265	0.30	0.055
0.950	300	0.30	0.052
0.950	325	0.30	0.050
0.950	400	0.30	0.045
0.950	250	0.35	0.059
0.950	300	0.35	0.054
0.950	325	0.35	0.052
0.950	400	0.35	0.047

A sample size of 250 to 400 patients produces a 2-sided 95% confidence interval with a distance from the proportion to the limits ranges from 0.042 to 0.059 when the estimated proportion varies from 0.25 to 0.35 (nQuery Advisor version 7.0).

In the HAWK and HARRIER studies, the proportion of naïve nAMD patients treated with brolucizumab who had disease activity at Week 16 was 30% less than for patients treated by aflibercept.

To determine a similar 30% proportion of patients with no disease activity at Week 16 in this pretreated study with a precision of 5.5% and alpha 5% (2-sided 95% confidence interval of width 11%), a total of 265 patients have to be observed in this study.

Considering a dropout rate of 10%, a total of 295 patients will be included.

13 Ethical considerations and administrative procedures

13.1 Regulatory and ethical compliance

This clinical study was designed and shall be implemented, executed and reported in accordance with the ICH Harmonized Tripartite Guidelines for GCP, with applicable local regulations (including European Directive 2001/20/EC, US CFR 21), and with the ethical principles laid down in the Declaration of Helsinki.

13.2 Responsibilities of the Investigator and IEC

Before initiating a study, the Investigator/institution must obtain approval/favorable opinion from the IEC for the study protocol, written ICF, consent form updates, patient recruitment procedures (e.g. advertisements) and any other written information to be provided to patients. Prior to study start, the Investigator is required to sign a protocol signature page confirming his/her agreement to conduct the study in accordance with these documents and all of the instructions and procedures found in this protocol and to give access to all relevant data and records to Novartis monitors, auditors, Novartis Quality Assurance representatives, designated agents of Novartis, IECs, and regulatory authorities as required.

If an inspection of the study site is requested by a regulatory authority, the Investigator must inform Novartis immediately that this request has been made.

13.3 Publication of study protocol and results

The protocol will be registered in a publicly accessible database such as clinicaltrials.gov and as required in EudraCT. In addition, after study completion (defined as last patient last visit) and finalization of the study report the results of this study will be submitted for publication and posted in a publicly accessible database of clinical study results, such as the Novartis clinical study results website and all required Health Authority websites (e.g. clinicaltrials.gov, EudraCT, etc.).

For details on the Novartis publication policy including authorship criteria, please refer to the Novartis publication policy training materials that were provided to you at the study Investigator meetings.

13.4 Quality control and quality assurance

Novartis maintains a robust Quality Management System (QMS) that includes all activities involved in quality assurance and quality control, to ensure compliance with written Standard Operating Procedures as well as applicable global/local GCP regulations and ICH Guidelines.

Audits of study sites, vendors, and Novartis systems are performed by auditors, independent from those involved in conducting, monitoring or performing quality control of the clinical study. The clinical audit process uses a knowledge/risk based approach.

Audits are conducted to assess GCP compliance with global and local regulatory requirements, protocols and internal SOPs, and are performed according to written Novartis processes.

14 Protocol adherence

This protocol defines the study objectives, the study procedures, and the data to be collected on study participants. Additional assessments required to ensure safety of patients should be administered as deemed necessary on a case by case basis. Under no circumstances including incidental collection is an Investigator allowed to collect additional data or conduct any additional procedures for any purpose involving any investigational drugs under the protocol, other than the purpose of the study. If despite this interdiction prohibition, data, information, observation would be incidentally collected, the Investigator shall immediately disclose it to Novartis and not use it for any purpose other than the study, except for the appropriate monitoring on study participants.

Investigators ascertain they will apply due diligence to avoid protocol deviations. If an Investigator feels a protocol deviation would improve the conduct of the study this must be considered a protocol amendment, and unless such an amendment is agreed upon by Novartis and approved by the IEC and health authorities, where required, it cannot be implemented.

5.3	Laboratory parameters derivations	35
5.4	Statistical models	35
5.5	Rule of exclusion criteria of analysis sets	36
6	Reference	38

List of abbreviations

AE	Adverse event
ATC	Anatomical Therapeutic Classification
BCVA	Best-Corrected Visual Acuity
CNV	Choroidal Neovascularization
CI	Confidence Interval
CRO	Contract Research Organization
CSFT	Central Sub-Field Retinal Thickness
CRT	Central Retinal Thickness
CSR	Clinical Study report
ENR	Enrolled set
FAS	Full Analysis Set
ECS	Edit checks specification
eCRF	Electronic Case Report Form
ICF	Informed Consent Form
IVT	Intravitreal
KM	Kaplan-Meier
MedDRA	Medical Dictionary for Drug Regulatory Affairs
nAMD	Neovascular Age-Related Macular Degeneration
OCT	Optical Coherence Tomography
PK	Pharmacokinetics
PD	Protocol deviation
PDS	Programming Datasets Specifications
PPS	Per-Protocol Set
PT	Preferred Term
q12w	Every 12 Weeks
SAP	Statistical Analysis Plan
SAF	Safety analysis set
SD-OCT	Spectral Domain Optical Coherence Tomography
SOC	System Organ Class
TFL	Tables, Figures, Listings
TtC	Treat-to-Control
USM	Urgent Safety Measure
WHO	World Health Organization

1 Introduction

The purpose of this Statistical Analysis Plan (SAP) is to describe the implementation of the statistical methods for all safety and efficacy analyses planned (Protocol-Section 12) in the clinical protocol (CRTH258AFR03, version no: 05, release date 05Apr2022). This document will be used to prepare the statistical results and the corresponding Clinical Study Report (CSR).

The details of CSR deliverables (shells for tables, figures and listings) and further programming specifications will be described in the Tables, Figures & Listings (TFL) shells and Programming Datasets Specifications (PDS) respectively, which will be included in this document.

Data will be analyzed by Novartis and/or the designated Contract Research Organization (CRO). Statistical software SAS version 9.4 or higher will be used for generating TFLs.

1.1 Study design

This is a prospective, single-arm, open-label, multicenter study to evaluate the efficacy and safety of brolucizumab 6 mg in pretreated suboptimal anatomically controlled patients with nAMD.

Approximately 295 adult patients will be screened and included (10% dropout rate expected) in France.

Before inclusion in the study, a patient must have a washout period of 4 weeks to 8 weeks (from 26 to 62 days inclusive) *versus* his/her last administration of a licensed anti-VEGF drug (i.e. Lucentis®, Eylea®).

The maximum study duration for 1 patient is 48 to 50 weeks, according to the patient schedule.

[figure not shown]
The study will consist of 2 periods ([Figure 1-1](#)):

- Open-label Treatment Period (from Screening/Baseline (Day 1) to Week 44 or Week 46 according to patient schedule)
- Follow-up Period (from Week 44 to Week 48 or from Week 46 to Week 50 according to patient schedule)

According to the patient treatment schedule, the last treatment can be at Week 44 or Week 46. If the last treatment visit is at Week 46, the End-of-study visit will be at Week 50 (at least 4 weeks after the last injection) instead of at Week 48.

Patients will require attending 5 mandatory study visits: Screening/Baseline (Day 1), Weeks 4, 8, 16, and 48/50. The other visit time points will depend on the injection regimen of the patient.

Figure 1-1 Study design

a End of treatment: Week 38/40/42/44/46 according to treatment schedule.

b End of study: at least 4 weeks after the end of treatment. For patients receiving the last IVT at Week 46, the EOS Visit will be at Week 50, 4 weeks following their last treatment.

The fellow eye will be treated at the discretion of the Investigator.

The Screening Visit and the Baseline Visit are the same visit in this study. Patients will receive 3 initial doses every 4 weeks (Day 1, Week 4 and Week 8). From Week 8, based on Investigator's judgment of visual and/or anatomic outcomes, the injection interval can be maintained on Q4 regimen or extended by 4 weeks at a time if there is no disease activity, as per Investigators decision, e.g. no change in visual acuity and in other signs of the disease (e.g. IRF, SRF, hemorrhage, leakage, etc.). If disease activity recurs, the injection interval should be shortened accordingly by 4 weeks at a time or to a minimal interval of 4 weeks.

Patients who show disease activity at any of visits after week 8 will be adjusted to treatment interval and will remain on this interval until the end of the study at Week 48/50.

At the Investigator's discretion, in case of interval extension, inspection visits can be performed at the midterm of the interval extension, e.g. 6 weeks after the last injection when the injection interval is extended from 4 weeks to 8 weeks. If there is no disease activity in the study eye at the inspection visit, as assessed by the Investigator, no treatment will be administered at this inspection visit; the next visit and injection will take place 2 weeks later, i.e. 8 weeks after the previous study treatment. If disease activity is observed by the Investigator in the study eye at the inspection visit, the study treatment will be administered by the Investigator; the injection interval will be reduced to 4 weeks and the next visit will be 4 weeks after the inspection visit. Similarly, inspection visits 10 weeks and 14 weeks after the last injection can be performed when the injection interval is extended from 8 weeks to 12 weeks and from 12 weeks to 16 weeks, respectively.

1.2 Study objectives and endpoints

Table 2-1 Objectives and related endpoints

Objectives	Endpoints
Primary objective	Endpoint for primary objective
• To evaluate the effect of brolucizumab 6 mg on disease control	• Proportion of patients with no disease activity at Week 16
Secondary objectives	Endpoints for secondary objectives
• To evaluate the long term effects of brolucizumab 6 mg on disease control	• Proportion of patients with no disease activity at Week 48
• To evaluate the effect of brolucizumab 6 mg on anatomical parameters	• Change from Baseline in CSFT as assessed by OCT over time up to Week 48 • Absence of IRF, SRF, and sub-RPE fluid as assessed by OCT over time up to Week 48 • Proportion of patients with a dry retina (neither IRF nor SRF) up to Week 48
• To evaluate the durability of brolucizumab 6 mg	• Distribution of the last interval with no disease activity up to Week 48 • Distribution of the maximal intervals with no disease activity up to Week 48
• To evaluate functional outcomes	• Average change in BCVA from Baseline up to Week 48
• To assess the safety and tolerability of brolucizumab 6 mg	• Incidence of AEs (serious and non-serious) up to Week 48

AEs=adverse events, BCVA=best corrected visual acuity, [REDACTED] CSFT=central sub-field retinal thickness, [REDACTED] IRF=intraretinal fluid, OCT= optical coherence tomography, [REDACTED]
SRF= subretinal fluid.

2 Statistical methods

2.1 Data analysis general information

Patients who consent and meet all the inclusion and none of the exclusion criteria will be screened to evaluate eligibility. After confirmation of eligibility, patients will be included and treated with brolucizumab 6 mg and data will be analyzed.

All categorical data will be presented in terms of frequencies and percentages. Summaries of continuous data will be presented in terms of n (the number of non-missing data points), mean, standard deviation (SD), median, lower and upper quartiles, minimum and maximum, the number of missing data points.

For descriptive statistics, the following rules for number of decimal places will be applied: arithmetic mean, median, lower quartile and upper quartile to 1 more decimal places than the raw data; minimum and maximum to the same number of decimal places as the raw data and SD, SE and 95% CI to 2 more decimal places than the raw data. Percentages will be presented to 1 decimal place.

2.1.1 General definitions

[figure not shown]
Study treatment: This is a single-arm study and all patients will be treated with brolucizumab 6 mg. Three loading injections (at Screening/Baseline/Day 1, Week 4 and Week 8), followed by a Treat-to-Control (TtC) regimen phase based on disease activity from Week 8 up to Week 44/46 (according to the treatment regimen). The investigator can individualize treatment intervals depending on disease activity, to adjust patient's injection regimen.

Study treatment start and end date: Study treatment start date is defined as the first date study treatment is administered and recorded on the Treatment Administration Record (DAR) Electronic Case Report Form (eCRF) page. Similarly, study treatment end date is defined as the last date of study treatment is administered and recorded on the Study Treatment Completion eCRF page.

Generally, study Day 1 is considered as the day of inclusion of the patient. However in this study, treatment is intended to be administered on the same day or if this is not possible, within 3 days after the day of inclusion of the patient.

Study day will be calculated as ((event date – study treatment start date) + 1 day) for events that occurred on or after study treatment start date (e.g. visit, AEs). For events prior to study treatment start date (e.g. time since diagnosis), study day will be negative and calculated as (event date – study treatment start date).

Baseline and post-baseline: Baseline value refers to the value of the last non-missing measurement collected prior to administration of the first dose of study treatment (Screening or Baseline visit).

A “post-baseline” value refers to a measurement taken after the first dose of study treatment. When assessments and treatments take place on the same day, treatment must occur after completion of the efficacy assessments and pre-injection safety measures (tonometry, slit lamp

[REDACTED]). If study visit assessments and the corresponding treatment occur on separate days, a repeat safety check-up will be performed prior to treatment of the eye and results documented in the source documents. More post-baseline safety measurements will be recorded in source document; visit window will be applied to OCT and IVT visits.

Change from Baseline: The difference of measure between post-baseline and Baseline is called change from Baseline.

Percent change from Baseline: The percent change from baseline will be calculated as below: $((\text{post-baseline value} - \text{Baseline value}) / \text{Baseline value}) * 100$.

Proportion: A proportion refers to the fraction of the total that possesses a certain attribute. In this study attribute is disease free activity.

Disease control: When patients have no disease activity after taking study treatment then patient will be consider as disease control.

On-treatment period: The on-treatment period lasts from the date of first administration of study treatment to 30 days after the date of the last actual administration of any study treatment.

Treatment duration: The maximum planned duration of treatment for each patient is 44 to 46 weeks in accordance with the designated treatment regimen. Discontinuation of study treatment for a patient occurs when study treatment is stopped earlier than the protocol planned duration and can be initiated by either the patient or the investigator.

Treatment discontinuation: When patients discontinue study treatment but continue in the study, the efficacy data will be used at the time the patient stopped study treatment.

Last interval: The last treatment interval (defined by the investigator) before Week 48.

Maximum interval: The longest interval of treatment reached by the patient over the study period.

Event for no disease activity: When patients will be with no disease status as per investigator decision after last dose in initiation phase then the patients will consider as event for no disease activity. If patients with active disease status or early discontinue then patients will be considered as censored for disease activity.

Dry retina: Absence of fluid (IRF/SRF/ sub-RPE) will be considered as dry retina.

Event for dry retina: When patients have absence of fluid then it will be considered as an event of dry retina. If patients have a presence of fluid before/at EOS or early discontinuation then will be censored.

[figure not shown]
Study eye and fellow eye: The investigator selects the eye with the worse BCVA at Screening as the study eye if both eyes are eligible as per the inclusion and exclusion criteria, unless the investigator deems as a study eye more appropriate to select the eye with better BCVA, based on medical reasons or local ethical requirements. If both eyes are eligible as per the inclusion and exclusion criteria, then it is recommended to select the right eye as the study eye.

The fellow eye will be examined only at Screening/Baseline and Week 48/EOS visits. Only best corrected near visual acuity (BCNVA) for the fellow eye will be analyzed. It is not requested for the purpose of this study to do any self-assessment measure of the fellow eye.

Disease activity criteria: Disease activity criteria will be assessed by the investigator based on whether nAMD is still active or has been re-activated. Guidance for the investigator is as follows (disease is active if at least one of the following criteria is observed by the investigator):

- BCVA decrease \geq 5 letters from the best value since Baseline due to disease activity.
- Any significant increase in CRT (based on investigator assessment).
- Retinal hemorrhage.
- Intraretinal fluid or SRF due to disease activity (degenerative cysts allowed).
- Increase of sub-RPE fluid.

These criteria are for guidance only, the investigator may define disease activity based on his/her own assessment.

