For all patients completing the study as per protocol, the End-of-Study (EOS) assessment will be performed at Week 48 (or Week 50 for patients receiving their last treatment at Week 46), at least 4 weeks (\pm 7 days) following the last possible study treatment administration. For patients who receive their last IVT at Week 46, the EOS assessment will be performed at Week 50 (\pm 7 days), at least four weeks (\pm 7 days) following their last possible study treatment administration. For clarity reason, the EOS visit will be named Week 48 in the rest of this protocol.

Patients withdrawn from the study prior to study completion will be asked to return for an early discontinuation (EOS) visit, 4 weeks (\pm 7 days) following their last study treatment administration. For early treatment discontinuations (ETD) refer to [Section 9.1.1](#).

4 Rationale

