14) The week 48/50 EOS assessments only apply to patients who completed the study per protocol. The assessments are not required for subjects who have undergone ETD assessments and continued in the study without study treatment.

15) ETD: Early treatment discontinuation applies to subjects who discontinue early from study treatment and continue in the study. The assessments should be performed 4 weeks after the last injection of study drug. This can occur at any time point.

16) For patients who continue in the study after ETD and up to Week 48/50 (end of study) while patient is on standard of care. Additional safety assessments and imaging can also be performed if required, as per investigators discretion. In addition, after ETD, subjects are not required to attend the mandatory visits at Week 16 and Week 48/50. The last visit should be at week 48. This can occur at any time point.

Assessments in the fellow eye

The fellow eye will be examined (data collected and analyzed) only at the Screening/Baseline and the Week 48/EOS visits as follows:

- At Screening/Baseline: BCVA, ophthalmic examination, [REDACTED] OCT, [REDACTED].
- At Week 48/EOS: BCVA, ophthalmic examination, [REDACTED] OCT [REDACTED].

Other assessments of the fellow eye may be performed at the Investigator's discretion in accordance with routine practice at other time points; however, these will not be collected or analyzed in this study.

All data obtained from these assessments must be supported in the patient's source documentation.

Concerning Odysight® optimal self-assessment, only best-corrected near visual acuity (BCNVA) for the study eye will be analyzed. It is not requested for the purpose of this study to do any self-assessment measure of the fellow eye.

Unscheduled visits

For patients who return to the study site before the next scheduled study visit, the Investigator will capture the unscheduled visit in the eCRF only in the case of a clinically significant abnormality finding.

If this finding leads to an AE and/or the decision to treat the patient prior to the next scheduled treatment, all the procedures listed for the interim visit need to be conducted and captured in the eCRF.

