2.9.1 Adverse events

All information obtained on AEs will be displayed by patient Summary tables for AEs will summarize only on-treatment events, with a start date during the on-treatment period ([see Section 2.1.1](#)) for definition of on-treatment period).

The count of treatment-emergent AEs, number (and percentage) of patients with treatment-emergent AEs (defined as events started after the first dose of study treatment or events present prior to start of study treatment but increased in severity based on PT) will be summarized in the following ways:

- By primary SOC and PT.
- By primary SOC, PT and maximum severity.

Separate summaries will be provided for study treatment related AEs, study procedure related AEs, need of USM, death, SAEs, other significant AEs action taken leading to study treatment withdrawn and AEs leading to dose interval adjustment (interval increase, interval reduce).

Adverse events will be summarized by presenting, the number and percentage of patients having any AE, having an AE in each primary SOC and having each individual AE (PT). Summaries will also be presented for AEs by severity. Summaries for AE will be presented for study treatment and procedure related to AEs. If a patient reported more than one AE with the same PT, the AE with the greatest severity will be presented. SOC will be presented in alphabetical order, preferred terms will be sorted within SOC in descending frequency of AEs. If a patients reported more than one AE within the same primary SOC, the patient will be counted only once with the greatest severity at the SOC level, where applicable. The AE will be presented in separate sections of ocular and non-ocular. For ocular then it will be presented by study eye, fellow eye, and any eye.

For the legal requirements of ClinicalTrials.gov and EudraCT, 2 required tables on treatment emergent AEs which are not SAEs with an incidence greater than 5% and on treatment emergent SAEs and SAEs suspected to be related to study treatment will be provided by system organ class and PT on the safety set population.

If for a same patient, several consecutive AEs (irrespective of study treatment causality, seriousness and severity) occurred with the same system organ class and PT:

- A single occurrence will be counted if there is ≤ 1 day gap between the end date of the preceding AE and the start date of the consecutive AE.

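### The final SAP closes the AE tables 30 days after the last injection, following one of two conflicting protocol definitions, so they do not give AE incidence up to Week 48 and can omit late treatment-stopping IOI/RV/RO

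*SAP*

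**What the plan says.** **Final SAP.** Section 2.1.1: "The on-treatment period lasts from the date of first administration of study treatment to 30 days after the date of the last actual administration". Section 2.9.1: "Summary tables for AEs will summarize only on-treatment events, with a start date during the on-treatment period". The same section describes treatment-emergent AEs as "defined as events started after the first dose of study treatment" (or worsening afterwards) and gives no end date. Section 2.9.1.1 plans AESI counts, rates and timing plots without naming a window. Section 4 declares no change to the protocol's analyses.

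**Protocol, two definitions.** Section 12.5.5 ends the on-treatment period 30 days after the last injection and adds that "summary tables for adverse events of special interest (AESIs) will summarize only on-treatment events". Section 12.5.5.1 ends it at "30 days after the last administration of study treatment or EOS whichever is the latest".

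**Endpoint.** Both documents list the safety endpoint as "Incidence of AEs (serious and non-serious) up to Week 48" (protocol Table 2-1; SAP 1.2).

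**Data collection.** Protocol 9.1.1 collects AEs and SAEs until at least Week 48 after an early treatment stop, and the post-ETD column of Table 8-1 includes AEs. Protocol 10.1.4 collects SAEs to the later of the last study visit or 30 days after the last dose. Protocol 10.1.1, in contrast, ends AE monitoring at 30 days.

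**Stopping rule.** Protocol 6.1.4 and 9.1.1 require study treatment to stop once IOI, including RV and/or RO, is confirmed.

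**Interim SAP.** Its section 2.1.1 uses 28 days.

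**The concern.** A 30-day tail is harmless while injections continue, because each new injection reopens the window. It matters for an event that itself ends treatment, since the preceding injection then becomes the last one. IOI/RV/RO is that kind of event, and it is the risk behind the trial's urgent safety measures. After Week 8 the inspection and treatment visits fall nominally 6 to 16 weeks after the last injection, all beyond day 30. An IOI first found at such a visit, with no earlier onset date recorded, would miss the AE tables.

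The omission can go in one direction only: incidence can be understated, not overstated. The planned summary of AEs leading to treatment withdrawal carries the same limit, so it could disagree with the disposition counts. If the limit also governs the plot of AESIs by time since last injection, treatment-stopping events would be cut at day 30 and the plot could not show whether late onset occurs.

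**Working it through.** The plan gives no figure of its own on this point to reproduce. The check is date arithmetic on nominal visit weeks, ignoring the ±7-day windows.

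**Inputs**
- Window end: last injection + 30 days (SAP 2.1.1).
- Intervals after Week 8: 8, 12 or 16 weeks (protocol 6.7.2.2).
- Planned last injection in completers: Week 38, 40, 42, 44 or 46 (footnote to the study design figure, protocol section 3).
- End of study: Week 48, or Week 50 if the last injection is at Week 46.

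**Step 1. Time outside the window before the next planned injection**, for an event that stops treatment: 7q − 30 days for an interval of q weeks.

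| Interval | Length (days) | Outside (days) | Share |
|---|---|---|---|
| Q8 | 56 | 56 − 30 = 26 | 46% |
| Q12 | 84 | 84 − 30 = 54 | 64% |
| Q16 | 112 | 112 − 30 = 82 | 73% |

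The 28-day loading interval lies inside the window.

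**Step 2. Time outside the window up to end of study**: max(0, 7 × (end week − week of last injection) − 30).

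| Last injection | Days to end of study | Outside (days) |
|---|---|---|
| Week 8 (early stop) | 280 | 250 |
| Week 14 (early stop) | 238 | 208 |
| Week 16 (early stop) | 224 | 194 |
| Week 38 (completer) | 70 | 40 |
| Week 40 (completer) | 56 | 26 |
| Week 42 (completer) | 42 | 12 |
| Week 44 (completer) | 28 | 0 |
| Week 46 (completer, Week 50) | 28 | 0 |

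**Step 3. The protocol 12.5.5.1 window.** Taking the later of 30 days or EOS, with EOS at end of study, the gap is 0 for every patient followed to that point.

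**Step 4. Selectivity.** Take two AEs, each starting on day 45 after a Q8 injection. One does not stop treatment: the day-56 injection follows, the window extends, and the AE is counted. The other is a confirmed IOI: no injection follows, the window closed on day 30, and the event is not in the AE tables.

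**Step 5. Effect of one omission.** Assuming all 295 planned patients are treated, each omitted patient lowers a reported incidence by 1/295 = 0.34 percentage points.

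**The case against.** **The SAP follows the protocol.** Section 12.5.5 has the same 30-day rule, names AESI tables, and states the safety endpoint there without a Week 48 limit. Protocol 10.1.1 also stops monitoring at 30 days. This stands: the SAP has not simply departed from the protocol. The defect is a contradiction within the protocol, resolved in the SAP without being recorded. A 30-day on-treatment table is a legitimate display and should stay.

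**Late events are not lost.** This also stands. SAP 2.9.1 lists treatment-emergent AEs by system organ class, preferred term and verbatim term, with dates, severity, relationship, action taken and outcome. SAP 2.9.1.1 adds an AESI listing, and protocol 12.5.5.1 lists all collected AEs. A late retinal vasculitis would be identifiable. What is missing is its place in the summary counts, and a listing does not give an incidence.

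**Later events may belong to another drug.** After the ETD visit, patients may receive standard-of-care anti-VEGF injections. This calls for flagging, and for care with the rate per 1000 injections.

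**A stronger reading to avoid.** A reader might infer that even the 12.5.5.1 window fails, because "Patients withdrawn from the study prior to study completion will be asked to return for an early discontinuation (EOS) visit, 4 weeks" after their last treatment, and "The week 48/50 EOS assessments only apply to patients who completed the study per protocol". The documents do not support this. The first sentence (protocol section 3) concerns patients withdrawn from the study, and the next one refers treatment discontinuers to 9.1.1. Table 8-1 footnote 15 calls their 4-week visit ETD. Footnote 16 follows them up to Week 48/50, described there as end of study. Footnote 14 and section 9.1.1 settle which assessments are needed; they do not move the end of study. The wording in section 8, Table 8-1 and 9.1.1 is loose enough that the end point should still be stated.

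**Conclusion.** The concern holds as a mismatch between window and endpoint and should be fixed. The AE tables as specified do not give incidence up to Week 48, and among late events they selectively omit those that stop treatment. The time outside the window is 46% to 73% of a maintenance interval. Up to end of study it is 194 to 250 days after an early stop at Week 8, 14 or 16, 12 to 40 days for completers last injected at Week 38 to 42, and none for Week 44 or 46.

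These figures rest on nominal visit dates and measure time, not events. The documents give no onset distribution, so the number of events lost is unknown and may be zero. It would be wrong to infer that the AESI rate is certainly understated: SAP 2.9.1.1 states no window, and whether the limit reaches the AESI outputs depends on reading it with its parent section and protocol 12.5.5. IOI without RV or RO has required discontinuation only since Amendment 4; any such event followed by another injection stays in the tables. The primary endpoint is unaffected.

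**What to change.** **Reconcile and record.** Align protocol 12.5.5 with 12.5.5.1, and 10.1.1 with 9.1.1 and 10.1.4. Record the chosen window in SAP section 4.

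**In the final SAP:**
- Report AE and AESI counts and percentages, and the AESI timing plots, from first injection to the later of 30 days after the last injection or the last study contact up to Week 48/50. State that for patients who stop treatment but stay in the study, the end point is this last contact and not the ETD visit.
- Keep the 30-day on-treatment tables alongside.
- Give the treatment-emergent definition a matching end date, so that the registry tables use a known window, and state the window in 2.9.1.1.
- Flag events starting after a switch to another anti-VEGF. Exclude them from the AESI rate per 1000 injections, whose denominator is brolucizumab injections, or show that rate separately.

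**In the final report,** note that the interim analysis, already performed, was planned with a 28-day window.

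**Cost.** One extra set of tables from data that protocol 9.1.1 and 10.1.4 already collect, plus documentation of the reconciliation. Changing the protocol text needs a written amendment under 14.1. Ocular capture after ETD is weaker, because contact may be by telephone or email and Table 8-1 schedules no ophthalmic examination or OCT at those visits. The report should say so.
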